12.3.2. Pharmacokinetic Analysis Set

The PK analysis set will consist of all subjects in the safety analysis set for whom at least 1 of the primary PK parameters can be calculated, and who have no major protocol deviations thought to impact on the analysis of the PK data. All the eligible PK data will be presented for each treatment using descriptive statistics. For the formal relative bioavailability evaluations, only subjects who provide eligible PK data for both Test and Reference treatments can be included for each comparison.

Pharmacokinetic data for a subject during any treatment period may be excluded from the corresponding descriptive and formal statistics as a result of the following:

- an AE of vomiting occurring at or before median t_{max} for that treatment,

- a pre-dose concentration of verinurad $> 5\%$ of C_{max} for that treatment.

If either of these occur for any subject during all treatment periods then the subject will be excluded from the PK analysis set.

Individual PK concentration data may be excluded from the PK analysis and/or statistical analyses and corresponding figures. The exclusion of any subjects from the PK analysis set, of any individual concentration-time points from the calculation of the PK parameters or from the statistical analyses and corresponding figures and of any individual PK parameters from the statistical analyses and corresponding figures will be documented by the PK Scientist including the reasons for exclusion.

All available reportable concentration data and PK parameter data will be listed. Concentration or parameter data for subjects excluded from the statistical summaries or formal statistics will be presented in the corresponding individual concentration versus time or PK parameter figures but not in the corresponding summary figures.

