12.9.4. Statistical Analysis of Pharmacokinetic Data

For each individual relative bioavailability comparison the ratios of C_{max}, AUC_{0-t} and AUC will be calculated for Test:Reference using log transformed data.

The following comparisons of relative bioavailability (AUC, AUC_{0-t} and C_{max}) of verinurad will be performed:

- Treatment 2 versus 1 i.e., “A capsule, fasted” versus “ER8 capsule, fasted”
- Treatment 4 versus 1 i.e., “B capsule, fasted” versus “ER8 capsule, fasted”
- Treatment 3 versus 1 i.e., “A capsule, fed” versus “ER8 capsule, fasted”
- Treatment 5 versus 1 i.e., “B capsule, fed” versus “ER8 capsule, fasted”
- Treatment 4 versus 2 i.e., “B capsule, fasted” versus “A capsule, fasted”
- Treatment 5 versus 3 i.e., “B capsule, fed” versus “A capsule, fed”
- Treatment 3 versus 2 i.e., “A capsule, fed” versus “A capsule, fasted”
- Treatment 5 versus 4 i.e., “B capsule, fed” versus “B capsule, fasted”

Analyses will be performed using a linear fixed-effects analysis of variance model using the natural logarithm of AUC, AUC_{0-t} and C_{max} as the response variables, sequence, period and treatment as fixed effects, volunteer nested within sequence as a random effect. Transformed back from the logarithmic scale, geometric means together with confidence intervals (CIs) (2-sided 95%) for AUC, AUC_{0-t} and C_{max} will be estimated and presented. Also, ratios of geometric means together with CIs (2-sided 90%) will be estimated and presented.

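### A major protocol deviation confined to one period removes the subject's other periods from the PK analysis set; exclude by subject-period instead

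*Protocol*

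**What the plan says.** Protocol Section 12.3.2 builds the PK analysis set from subjects in the safety set who have at least one calculable primary PK parameter and "who have no major protocol deviations thought to impact on the analysis of the PK data". This condition is attached to the subject.

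Two other exclusions in that section are attached to the period. For vomiting at or before the median tmax, and for a pre-dose concentration above 5% of Cmax, "Pharmacokinetic data for a subject during any treatment period may be excluded from the corresponding descriptive and formal statistics". The whole subject goes only in the extreme case: "If either of these occur for any subject during all treatment periods then the subject will be excluded from the PK analysis set".

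For the formal comparisons, "only subjects who provide eligible PK data for both Test and Reference treatments can be included for each comparison".

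Section 12.9.4 names a "linear fixed-effects analysis of variance model" and gives its terms as "sequence, period and treatment as fixed effects, volunteer nested within sequence as a random effect". From it, "ratios of geometric means together with CIs (2-sided 90%) will be estimated and presented" for eight comparisons.

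Section 12.5 lists dosing deviations, among them a subject who was not fasted as required around a dose. Section 12.1 says that no separate SAP will be written, though changes may go into an abbreviated one.

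**The concern.** In a five-period single-dose crossover, many deviations belong to one period. A missed fast before one dose affects that dose's profile and no other, given adequate washout. If such a deviation is judged major and relevant to PK, the wording of Section 12.3.2 takes the subject out of the PK set, good profiles included. Vomiting, which can spoil a profile just as thoroughly, costs only its own period. The protocol gives no reason for the difference.

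Precision is at stake in a trial that randomises 25 to keep at least 20 evaluable subjects. Because no separate SAP is planned, this text is the working specification, and a data review meeting that follows it literally has to drop the subject.

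Two smaller uncertainties lie beside it. The text does not say whether the eight ratios come from one five-treatment model or from separate fits. The model is also labelled as fixed-effects although its subject term is random.

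**Working it through.** **Planned numbers.** Sections 7.3 and 9.9.2 give five sequences (12345, 23451, 51234, 34512, 45123) with 5 subjects each: 5 × 5 = 25 randomised and 5 × 4 = 20 evaluable. The basis for 20 is redacted in Section 12.4 and cannot be reproduced.

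**Assumptions.** The within-subject variance σ² is equal across treatments. The between/within variance ratio is 2. One subject in each of k sequences has one faulty period (period 3). The documents give no figure for any of these.

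**Method.** The variance of a contrast c is c′(X′V⁻¹X)⁻¹c, with sequence, period and treatment in X and a random subject effect in V. It is averaged over the eight comparisons in Section 12.9.4.

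**Complete data.** 2σ²/25 = 0.080σ². The model calculation returns the same value.

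**Whole-subject against by-period exclusion.**

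| Subjects with one faulty period | Profiles lost, by period | Profiles lost, whole subject | Valid profiles discarded | Mean variance ratio |
|---|---|---|---|---|
| 0 | 0 | 0 | 0 | 1.00 |
| 1 | 1 | 5 | 4 | 1.03 |
| 3 | 3 | 15 | 12 | 1.11 |
| 5 | 5 | 25 | 20 | 1.19 |

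For three subjects the mean variances are 0.0912σ² (whole subject) and 0.0824σ² (by period): 0.0912/0.0824 = 1.107. As a rough check, 22 complete subjects give 2σ²/22 = 0.0909σ². On the log scale the interval widens by about √1.107 = 1.052, ignoring the small change in the t quantile. Recalculating with variance ratios of 1, 1.5 and 4 leaves the three-subject figure at 1.107 to 1.108. It therefore depends on how many subjects are affected far more than on the variance components.

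**The pair rule (secondary).** The comparison is between one model on all eligible periods and two-treatment fits on pair-complete subjects, at an assumed CV of 25%.

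- 25 complete subjects: variance ratio 1.00. Residual df are 125 − 25 − 4 − 4 = 92 for one model and 50 − 25 − 1 − 4 = 20 for a pair fit. The 90% half-width factors are 1.123 and 1.128.
- One lost period: mean variance ratio about 1.01.
- Five subjects, one per sequence, leaving after period 3: mean variance ratio 1.06. The factors are 1.130 and 1.141, and ln 1.141 / ln 1.130 = 1.08.
- About 10% of periods lost, one random draw: mean variance ratio 1.10, largest 1.20. The factors are 1.132 and 1.147, and ln 1.147 / ln 1.132 = 1.11.

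If pair-complete subjects keep all their treatments in the fit, the mean variance ratios in the last two cases fall to about 1.05 and 1.08.

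**The case against.** The strongest reply is that the loss is not automatic. Whether a deviation is major and thought to affect PK is a judgement made at the data review meeting, under a separate deviation specification (Section 12.5). No passage classes an incomplete breakfast or a missed fast as major. Section 12.3.2 also lets individual PK parameters be excluded with documented reasons, which offers a narrower route. Subjects are resident and dosing is supervised, so such deviations should be few. The only completion figure in the document is 94.5%, from pooled Phase 1 studies (Section 5.2.3.1). No acceptance limit appears in the unredacted text, so no decision is shown to change. All of this limits the size of the problem. It does not alter the clause, which still removes the subject once the judgement is made.

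A reader might infer more than the documents support, in two ways.

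- *That PK exclusions in general act on whole subjects.* They do not. The vomiting and pre-dose rules act by period.
- *That the pair rule contradicts the random-subject model.* It does not. Such a model can be fitted to pair-complete data, and Section 12.9.4 never promises to use incomplete subjects. The random term also serves the 95% intervals for the treatment geometric means.

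Pair-complete analysis is defensible too. It keeps each ratio within subject and does not need one within-subject variance across fed, fasted and different formulations. Whether a pooled model should replace it is a matter on which statisticians differ. General methodology in Section 12.2 is largely redacted and may already settle how many models are fitted.

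**Conclusion.** The point holds for the major-deviation clause. Followed as written, it discards up to four valid profiles for each subject whose deviation touched one period, while comparable faults in the same section cost one profile. Contrast variance rises by about 3%, 11% and 19% on average for 1, 3 and 5 such subjects out of 25, and not at all if there are none. These figures rest on equal within-subject variance and the loss pattern described above. The plan gives no expected number of deviations.

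The pair rule is a loss of efficiency when periods are missing: about 1% to 10% in mean variance in the patterns tried, and none in variance with complete data. With missing periods, separate fits also need not give mutually consistent ratios (4 versus 1 divided by 2 versus 1 need not equal 4 versus 2), although each ratio remains valid. The fixed-effects label is editorial, since the role of every term is stated. This is a cheap improvement to the primary analysis text; nothing here invalidates the analysis.

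**What to change.** In Section 12.3.2, apply major-deviation exclusions to the subject-period when the deviation affects only that period. Keep whole-subject exclusion for deviations that affect all periods, such as an eligibility breach. The cost is a sentence or two, plus a period-by-period judgement at the data review meeting before hard lock.

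As secondary clarifications in Section 12.9.4:

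- state whether one five-treatment model or comparison-specific models supply the eight ratios;
- run a mixed model on all eligible subject-periods alongside the pair-complete analysis, noting that it assumes a common within-subject variance;
- call the model a linear mixed-effects model.

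These cost a few words and one extra run per parameter.

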12.4. Determination of Sample Size

CCI
[Redacted text block]

12.5. Protocol Deviations

Per Protocol set will be based on protocol deviations and it is defined as all subjects included in the safety analysis set with no major protocol deviations.

Protocol deviations are considered any deviation from the clinical study protocol relating to a subject, and include the following:

- Inclusion/exclusion criteria deviations.
- Dosing deviations (e.g., incorrect treatment received, subject was not fasted as per the protocol requirements prior to and after dosing).
- Time window deviations for safety and/or PK assessments.
- Subjects receiving prohibited concomitant medications.

- Other procedural and study conduct deviations recorded by the Clinical Unit on a protocol deviation log.

The criteria for the assessment and reporting of protocol deviations will be stipulated in a separate study specific protocol deviation specification document. This will include a Windows Allowance Document which stipulates tolerance windows for safety and PK assessments. Measurements performed within these tolerance windows will not be considered as protocol deviations and will not be reported.

Pharmacokinetic samples where the actual time of collection deviates by more than 10% from the protocol scheduled collection time will be included in the PK analysis to determine the PK parameters but will be excluded from the summary statistics and corresponding plots.

All protocol deviations will be discussed at the data review meeting prior to database hard lock in order to define the analysis sets for the study.

Important protocol deviations will be listed by subject.

Protocol deviations will be handled in accordance with PAREXEL SOPs.

For handling of protocol amendments, see Section 3.6.

12.6. Subject Disposition

A randomization listing will be presented and include the following: each subject's randomization number, the subject's full enrolment number, the treatment sequence to which the subject has been randomised and the country where the study centre is located.

Subjects and/or data excluded from the PK analysis set will be listed including the reason for exclusion. Subject disposition will be summarized and will include the following information: number of subjects randomised and dosed, number and percentage of subjects completing the study and the number and percentage of subjects who were withdrawn (including reasons for withdrawal). Disposition data will be presented based on all subjects randomised (subjects entered into the study that received a randomization number, prior to dosing).

Subject discontinuations will be listed including the date of study exit, duration of treatment and reason for discontinuation. A listing of informed consent response will also be presented.

12.7. Demographic and Baseline Data

Demographic variables (age, gender, race, ethnicity, height, weight and BMI) will be listed by subject. Demographic characteristics (age, gender, race and ethnicity) and subject characteristics (height, weight and BMI) will be summarized separately by treatment sequence

and overall for all randomised subjects. The denominator for percentages will be the number of randomised subjects.

Medical history data will be listed by subject including visit, description of the disease/procedure, Medical Dictionary for Regulatory Activities (MedDRA) System Organ Class (SOC), MedDRA Preferred Term, start date and stop date (or ongoing if applicable).

12.8. Prior and Concomitant Medication and Drug Administration

12.8.1. Prior and Concomitant Medication

Prior medications are those that started and stopped prior to the first dose of IMP; all medications taken after first dosing are considered as concomitant (including medications that started prior to dosing and continued after). Prior medication started within 3 months prior to the first dose of IMP will be recorded also in the concomitant medication module of

CCI

Prior and concomitant medication will be listed by subject and will include the following information: reported name, preferred term, the route of administration, dose, frequency, start date/time, duration and indication. Prior and concomitant medication will be coded according to the Sponsor's drug dictionary.

12.8.2. Drug Administration

Drug administration dates and times will be listed for each subject and treatment period. Details of high-fast, high-calorie breakfast will be listed.

12.9. Pharmacokinetic Analysis

12.9.1. Pharmacokinetic Parameters

Where possible, the following PK parameters will be determined for verinurad using plasma concentrations.

Primary PK parameters

AUC	Area under plasma concentration-time curve from time zero to infinity
AUC _{0-t}	Area under the plasma concentration-time curve from time zero to time of last quantifiable concentration
C _{max}	Maximum observed plasma concentration

Secondary PK parameters

AUC ₀₋₂₄	Area under the plasma concentration-time curve from time zero to 24 hours
t _{max}	Time to reach maximum observed plasma concentration

$t_{1/2\lambda z}$	Half-life associated with terminal slope (λz) of a semi-logarithmic concentration-time curve
CL/F	Apparent total body clearance of drug from plasma after extravascular administration (parent drug only)
MRT	Mean residence time of the unchanged drug in the systemic circulation from zero to infinity
t_{last}	Time to reach last quantifiable plasma concentration
V _{ss} /F	Apparent volume of distribution during the terminal phase after extravascular administration (parent drug only)
V _z /F	Apparent volume of distribution during the terminal phase after extravascular administration

The following diagnostic parameters for plasma PK analysis will be listed, but not summarized:

t lower	Start of exponential fit
t upper	End of exponential fit
λzN	Number of data points included in the log-linear regression analysis
Rs _q _adj	Regression coefficient adjusted for the λzN , Goodness-of-fit statistic for calculation of λz
%AUC _{extr}	Percentage of AUC obtained by extrapolating the area under the plasma concentration-time curve from the time of the last quantifiable concentration to infinity
λz	Terminal elimination rate constant

Additional PK parameters may be determined where appropriate.

12.9.2. Derivation of Pharmacokinetic Parameters

The PK analyses of the plasma concentration data for verinurad will be performed by Covance Clinical Pharmacokinetic Alliance on behalf of AstraZeneca R&D.

PK parameters will be derived using non-compartmental methods with Phoenix[®] WinNonlin[®] Version 8.1, or higher. All descriptive and inferential statistical computations will be performed using SAS[®] Version 9.4, or higher.

PK analysis will, where possible, be carried out using actual times recorded in the raw data. If actual times are missing, nominal times will be used.

Plasma concentrations which are NQ prior to the first quantifiable concentration will be set to a value of zero. After the first quantifiable concentration, any NQ plasma concentrations will

be set to missing for all concentration profiles. Where 2 or more consecutive concentrations are NQ at the end of a profile, the profile will be deemed to have terminated and therefore any further quantifiable concentrations will be set to missing for the calculation of the PK parameters unless it is considered to be a true characteristic of the profile of the drug.

If an entire concentration-time profile is NQ, the profile will be excluded from the PK analysis.

C_{max}, t_{max} and t_{last} will be taken directly from the plasma concentration-time profile.

Terminal elimination half-life, calculated as $(\ln 2)/\lambda_z$, will be estimated by log-linear least squares regression of the terminal part of the concentration-time curve. For the determination of λ_z , the start of the terminal elimination phase for each subject will be defined by visual inspection and will be the first point at which there is no systematic deviation from the log-linear decline in plasma concentrations (t_{lower}). The last point (t_{upper}) will be the time of the last quantifiable plasma concentration. A minimum of 3 data points will be used in calculating λ_z , and the duration of time over which λ_z is recommended to be at least 3 times the subsequently estimated terminal half-life. Where an elimination half-life is estimated over less than 3 times the subsequently estimated terminal half-life, it will be flagged and commented upon in the study report by agreement with the Sponsor.

The R_{sq_adj} value will be calculated to show the goodness-of-fit of the log-linear regression taking into consideration the number of points used in the estimation. To achieve a good precision in the estimation, the R_{sq_adj} value should be high, a value of ≥ 0.8 being indicative of good correlation. Any λ_z with a R_{sq_adj} of < 0.8 will be flagged in the data listings along with any parameters derived from λ_z (e.g., $t_{1/2}\lambda_z$, AUC, CL/F, V_z/F and %AUC_{extr}) and agreement reached with the Sponsor regarding any exclusion of data from the summaries.

AUC values, including AUC and AUC_{0-t}, will be calculated using the linear trapezoidal method when concentrations are increasing and the logarithmic trapezoidal method when concentrations are decreasing (linear up, log down method). AUC is estimated by $AUC_{0-t} + C_{last}/\lambda_z$ where C_{last} is the observed last quantifiable drug concentration. The AUC values where the percentage extrapolation is greater than 20% and any parameters dependent on AUC will be flagged in the data listings and agreement reached with the Sponsor on whether exclusions from the summary or formal statistics are required.

The minimum requirement for the calculation of AUC will be the inclusion of at least 3 consecutive plasma concentrations above the lower limit of quantification (LLOQ), with at least 1 of these concentrations following C_{max}.

Apparent clearance (CL/F) will be determined from the ratio of dose/AUC. Apparent volume of distribution based on the terminal phase (Vz/F) will be determined from the ratio of dose/ λ_z *AUC. Vss/F will be determined by multiplying CL/F by MRT.

12.9.3. Presentation of Pharmacokinetic Data

A listing of PK blood sample collection times, as well as derived sampling time deviations will be provided. Plasma concentrations will be summarized for the PK analysis set for each time point by treatment using the following descriptive statistics: n, n below LLOQ, geometric mean (gmean), geometric coefficient of variation [CV] (gCV%), arithmetic mean, arithmetic SD, gmean \pm geometric SD (gSD) (gmean + gSD and gmean - gSD), median, minimum (min) and maximum (max).

The gmean is calculated as the exponential(μ) where μ is the arithmetic mean calculated using log-transformed data.

The gCV% is calculated as $100 * \sqrt{\exp(s^2) - 1}$ where s is the SD of the log-transformed data.

The gmean \pm gSD (gmean - gSD and gmean + gSD) are calculated as $\exp[\mu \pm s]$.

Pharmacokinetic concentration data will be presented in the listings to the same number of significant figures as the data received from the bioanalytical laboratory (usually to 3 significant figures) and against the same units as received. Pharmacokinetic concentration descriptive statistics will all be presented to 4 significant figures with the exception of the min and max which will be presented to 3 significant figures and n and n < LLOQ which will be presented as integers.

Individual concentrations with time deviations of greater than $\pm 10\%$ from the protocol scheduled time will be used in the PK analysis but will be flagged for exclusion from the summary tables and corresponding figures.

Plasma concentrations that are NQ, Not Reportable or missing will be handled as follows:

Individual concentrations below the LLOQ of the bioanalytical assay will be reported as NQ in the listings with the LLOQ defined in the footnotes of the relevant tables, figures and listings. Individual plasma concentrations that are Not Reportable will be reported as no result (NR) and those that are missing will be reported as NS (No Sample) in the listings. Plasma concentrations that are NQ, NR or NS will be handled as follows for the provision of descriptive statistics:

- Any values reported as NR or NS will be excluded from the summary tables and corresponding figures.

- At a time point where less than or equal to 50% of the concentration values are NQ, all NQ values will be set to the LLOQ, and all descriptive statistics will be calculated accordingly.
- At a time point where more than half of the values are NQ, the gmean, gmean + gSD, gmean-gSD and gCV% will be set to not calculable (NC). The maximum value will be reported from the individual data, and the minimum and median will be set to NQ.
- If all values are NQ at a time point, no descriptive statistics will be calculated for that time-point. The gmean, minimum, median and maximum will be reported as NQ and the gCV% and gmean ± gSD as NC.
- The number of values below LLOQ ($n < \text{LLOQ}$) will be reported for each time-point together with the total number of collected values (n).

Three observations $> \text{LLOQ}$ are required as a minimum for a plasma concentration to be summarized. Two values $> \text{LLOQ}$ are presented as a minimum and maximum with the other summary statistics as NC.

All reportable plasma PK parameters will be listed for each subject and treatment. A separate listing will be provided for the diagnostic PK parameters.

Plasma PK parameters will be summarized for the PK analysis set by treatment using the following descriptive statistics:

- C_{max} , AUC, AUC(0-t), and AUC(0-24): present n, gmean, gmean + gSD, gmean-gSD, arithmetic mean, arithmetic SD, gCV(%), median, min and max.
- $t_{1/2\lambda z}$, CL/F, Vz/F, Vss/F and MRT: present n, gmean, gmean + gSD, gmean-gSD, arithmetic mean, arithmetic SD, gCV(%), median, min and max.
- t_{max} and t_{last} present n, median, min and max.
- Diagnostic parameters (e.g., λz , t upper, t lower, λz_N , Rsq_adj and %AUCextr): listed only and not summarized.

Three values are required as a minimum for PK parameters to be summarized. Two values are presented as a min and max with the other summary statistics as NC.

If one or more values for a given parameter is zero (or imputed with zero), then no geometric statistics will be calculated for that parameter and the results for geometric statistics will be set to NA (not applicable).

Pharmacokinetic parameter listings will be presented according to the following rules:

- C_{max} – present to the same number of significant figures as received from the bioanalytical laboratory.

- t_{max} , t_{last} , t_{lower} and t_{upper} – present as received in the data, usually to 2 decimal places.
- AUC, AUC(0-t), AUC(0-24), $t_{1/2}\lambda_z$, CL/F, V_z/F , V_{ss}/F , MRT, C_{max} , λ_z , %AUC_{extr}, R_{sq_adj} will be presented to 3 significant figures.
- $\lambda_z N$ – will be presented as an integer (no decimals).

The descriptive statistics for PK parameter data will all be presented to 4 significant figures with the exception of the min and max which will be presented to 3 significant figures apart from the following:

- t_{max} and t_{last} : –present as received in the data, usually to 2 decimal places.

Pharmacokinetic data (concentrations and parameters) from subjects excluded from the PK analysis set will be included in the data listings, but not in the descriptive statistics or in the inferential statistics as appropriate.

Individual subject plasma concentrations versus actual time will be plotted in linear and semi-logarithmic scale with all treatments overlaid on the same plot and separate plots for each subject.

Combined individual subject plasma concentration versus actual times will be plotted in linear and semi-logarithmic scale. Separate plots will be presented for each treatment.

Geometric mean plasma concentration (\pm gSD) versus nominal sampling time will be plotted in linear and semi-logarithmic (no SD presented) scale with separate plots for all treatments on the same figure and with the fasted and fed treatments on the same figure for each study formulation.

All gmean plots or combined plots showing all subjects by treatment will be based on the PK analysis set. Individual plots by subject will be based on the safety analysis set.

For consistency, the plasma concentration values used in the gmean data graphs will be those given in the descriptive statistics summary table for each time-point.

For gmean concentration-time plots, NQ values will be handled as described for the descriptive statistics; if the geometric mean is NQ, the value plotted will be zero for linear plots and missing for semi-logarithmic plots. Any $gmean \pm gSD$ error bar values that are negative will be truncated at zero on linear concentration-time plots and omitted from semi-logarithmic plots.

For individual plots, plasma concentrations which are NQ prior to the first quantifiable concentration will be set to a value of zero (linear plots only). After the first quantifiable concentration, any NQ plasma concentrations will be regarded as missing.

